- f. Urinalysis by dipstick; if results are abnormal, follow up with microscopy. Samples are to be collected under colored lighting into opaque containers to blind participants to any discoloration of the urine.
- g. For women of childbearing potential: Serum pregnancy test at screening.
- h. Body composition assessments by bioimpedance and physical measurements.
- i. Performed during screening as a secondary visit or up to Day -1 check-in to confirm subject is still eligible.
- j. Telemetry and oximetry will continue into approximately 24 hour timepoint (Day 2), although it may be interrupted as needed to allow subjects to bathe.
- k. Plasma PK samples will be drawn at pre-dose (time 0); post-dose on Day 1 at 0.25, 0.50, 1, 1.5, 2, 4, 6, 8, and 12hours; 24 hours post-dose (Day 2); 48 hours post-dose (Day 3); 72 hours post-dose (Day 4); and 96 hour post-dose (Day 5).
- l. Urine will be collected for PK analysis on Day 1 from a pre-dose void and post-dose from 0–4 hours, 4–8 hours, 8–12 hours, and 12–24 hours; from 24–48 hours post-dose; from 48–72 hours post-dose ; and from 72–96 hours post-dose . Samples are to be collected at intervals under amber-colored lighting into opaque containers to blind participants to any discoloration of the urine.
- m. Mandatory muscle biopsy on Day 2 only.
- n. IPSS questionnaire will be performed at the specified timepoints per SOA- results greater than 8 will necessitate an unscheduled urinary system ultrasound as soon as is feasible.
- o. Urinary system Ultrasound will be performed at specified timepoints in SOA unless the IPSS result (greater than 8) necessitates additional unscheduled ultrasonography.
- p. Screening eligibility will be determined by off-site (LabCorp) lab Total CK and CK-MB values and normal ranges while check-in eligibility will be determined by Day-1 on-site (WCT) lab Total CK and CK-MB values and normal ranges. Furthermore, CK isoenzymes (e.g., MM, MB) will not be evaluated as part of dose escalation decisions – rather total CK will be used.

	Screening	CI	CRU Inpatient															
Day	(-30 to -2)	D (-1)	D1												D2	D3	D4	D5
Hour			0	0.25	0.50	1	1.5	2	3	4	6	8	12	← Washout →				
Plasma PK ^k																		
Urine PK ^l			X							X		X	X	X	X	X	X	
Genetic biomarker (buccal swab)		X																
Plasma Biomarker			X			X								X				
Spirometry		X								X			X	X	X		X	
Electronic nerve stimulation response		X								X				X			X	
Dynamometry		X								X		X	X	X	X	X	X	

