- Laboratory assessments will include serum chemistry, hematology, liver function tests, coagulation, and creatinine kinase (CK-MM and CK-MB). eGFR will use CKD-EPI calculation
- Urinalysis by dipstick; if results are abnormal, follow up with microscopy. Samples are to be collected at intervals under colored lighting into opaque containers to blind participants to any discoloration of the urine.
- Telemetry and oximetry will continue for approximately 24 hours post-dose (Day 7) although it may be interrupted as needed to allow subjects to bathe.
- Plasma PK samples will be drawn at pre-dose (time 0); post-dose on Day 1 at 0.25, 0.50, 1, 1.5, 2, 4, 6, 8 and 12 hours; 24 hours post-dose (Day 7); 48 hours post-dose (Day 8); 72 hours post-dose (Day 9); and 96 hours post-dose (Day 10).
- Urine will be collected for PK analysis on Day 6 from a pre-dose void and post-dose from 0–4 hours, 4–8 hours, 8–12 hours, and 12–24 hours; from 24–48 hours post-dose; from 48–72 hours post-dose; and from 72–96 hours post-dose. Samples are to be collected at intervals under colored lighting into opaque containers to blind participants to any discoloration of the urine.
- Mandatory muscle biopsy on Day 7 (time 0) only.
- IPSS questionnaire will be performed at the specified timepoints per SOA- results greater than 8 will necessitate an unscheduled urinary system ultrasound as soon as is feasible.
- Urinary system Ultrasound will be performed at specified timepoints in SOA unless the IPSS result (greater than 8) necessitates additional unscheduled ultrasonography.

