2.5. Benefit/Risk Assessment

There will be no direct benefits to normal healthy volunteers being enrolled in this FIH study.

Safety is predicated on the enabling, nonclinical Good Laboratory Practice (GLP) safety and toxicology studies. In addition, during the clinical study, extensive safety evaluations of biochemical, hematologic, renal and urinary systems, cardio-respiratory parameters, as well as clinical evaluations, will be performed. A two-stage dosing strategy with sentinel participants will limit exposure to the investigational agent as dosing is advanced.

To fully evaluate the PK and pharmacodynamic (PD) aspects of MTR-601, subject's will be asked to undergo a single needle biopsy of skeletal muscle (vastus lateralis) using a Bard Magnum 12 gauge or functionally similar hand-held, spring-loaded device (in conjunction with local anesthesia and skin disinfection), potentially requiring 2 collections, which is minimally invasive and commonly used in clinical trials. The risks of such a procedure are discomfort/pain and possibly some small post-procedure bleeding. Any adverse reactions will be appropriately attended to by the unit medical staff.

The myosin-2 isoform is present in fast-twitch skeletal muscles and the extra-ocular muscles could be affected by MTR-601. Oculofacial AEs or any reduction in movement of the eyes, with potential for disconjugate gaze and/or possible "dizziness" or "imbalance" will be noted as an AESI. Additionally, AEs relating to swallowing or proximal muscle weakness (evaluated as part of the routine neurological examination) will be noted as an AESI. Nonclinical studies in the rat but not the dog showed urinary symptomatology not expected in humans, but out of an abundance of caution, any AE relating to difficulties in urination (evaluated with the IPSS questionnaire and urinary system ultrasound) will be noted as an AESI.

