3. OBJECTIVES AND ENDPOINTS

Objectives	Endpoints
Primary	
To assess the safety and tolerability of single and multiple doses of MTR-601 in normal healthy volunteers under fed and fasted conditions.	
The primary endpoint is safety assessed after single and multiple dose administration by:
 
 • Incidence, severity, and relatedness of adverse events (AEs; number and incidence of treatment-emergent adverse events [TEAEs]) • Incidence of laboratory abnormalities, based on hematology, clinical chemistry, coagulation, urinalysis test results • Vital sign measurements • 12-lead electrocardiograms (ECGs) • Echocardiography • Physical and neurological examinations • Telemetry and oximetry • Spirometry • Urinary system Ultrasound
Secondary	
To evaluate the plasma and urine pharmacokinetics (PK) of MTR-601	
Pharmacokinetic evaluations may include:
 
 • Concentration-time relationships • Estimations of dose proportionality at steady state • Estimation of time to achieve steady state • Potential MTR-601 metabolites
	
Exploratory	

Muscle accumulation of MTR-601 by muscle biopsy and other potential mechanistic, predictive and PD markers of MTR-601	
• An evaluation of concentration-effect relationships with other parameters (e.g., cytochrome P450 isoenzymes that affect absorption, distribution, metabolism, and excretion [ADME], other muscle parameters, gender, etc.) that may be performed at a later date and described in a stand-alone analysis plan and report• Muscle accumulation assessed by muscle biopsy and estimates of body muscle mass• An evaluation of potential MTR-601 PD and/or predictive biomarkers may be conducted (genetic and/or protein endpoints)
---	---

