- Subjects in the SAD Level 2 Two-Dose (20mg) will be dosed in a fasting state on Day 1 with a subsequent 4-day washout period, followed by dosing in a fed state (standard not-high fat breakfast) on Day 6.
- SAD Level 4 (80 mg) dosing is optional and may be adjusted based upon PK and safety results from earlier cohorts.
- Subjects may be enrolled in small groups to accommodate clinic scheduling.

MAD Levels 1–6 dosing:

- The MAD portion of the study will commence at MAD Level 1 (10 mg) after the safe completion of the subjects in at least the 2 SAD Level 2 Two-Dose cohort.
- Subjects in MAD Levels 1–6 will be dosed in a fed state (standard non-high-fat breakfast) over 14 continuous days of dosing.
- MAD cohorts may be enrolled in small groups to accommodate clinic scheduling with subjects dosed in a staggered fashion.

Dose Escalation:

The study will be monitored by a Safety Review Committee (SRC) comprised of the Principal Investigator (PI), the Medical Monitor, and the Sponsor. The SRC is intended to ensure treatment does not pose undue risk to subjects. Dose escalation to the next higher dose level cohort will not take place until the SRC has assessed the data from at least 7 out of 8 subjects/cohort through discharge (supplemental plasma PK information on a previously treated cohort may be requested as a part of the review) and determined that adequate safety and tolerability has been demonstrated to permit proceeding.

The planned dose levels for MAD Cohort 5 (80 mg) and Cohort 6 (160 mg) may be decreased based on the plasma PK from the preceding MAD cohort. Escalation will proceed no higher than a dose that is estimated to yield $\leq \frac{1}{2}$ of the rate 28-day NOAEL exposure ($C_{\max} \leq 421$ ng/mL, $AUC_{0-24} \leq 6,600$ ng*hr/mL).

The SRC may recommend:

- Ascending to the planned next higher dose level
- Ascending to a dose level lower than the planned next higher dosage level cohort
- Repeat dosing at the current dose level
- Descending to an intermediate dose above a previously tolerated dose level
- Pausing dose escalation
- Stopping the study

Participation in the clinical study may be discontinued by an Investigator (or delegate) in charge of the study or by the Sponsor for any of the following reasons in [Table 5](#).

Table 5: Stopping Rules

Stopping Rules ^d	Individual Subject Stopping Rules ^a	Cohort and/or Dose Escalation Stopping Rules
ALT or AST $\geq 3 \times$ ULN	≥ 1 subject	N/A

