5.3 Conventions

QMD Ref: Worldwide-TMP-ST-054-1.0_Effective: 12Aug2022	Governing QMD: Worldwide-SOP-ST-026
Confidentiality Statement This document is the property of Worldwide Clinical Trials Inc. and may not be duplicated, copied, altered or removed from company without prior approval from Worldwide Quality Assurance or in compliance with Worldwide Standard Operating Procedures.	

Worldwide Clinical Trials Controlled Quality Management Document			
		Sponsor:	MTR-601-NHV-101
		Protocol Number:	Motric Bio
STATISTICAL ANALYSIS PLAN			

All safety data listings, summaries, figures and statistical analyses will be generated using SAS version 9.4 or higher².

Summaries will be presented by treatment cohort or overall.

Treatment labels will be displayed as follows: For SAD

Presentation 1: For on and/or after treatment summaries

MTR-601					
Placebo	Cohort 1	Cohort 2	Cohort 3	Cohort 4	Cohort 5
(N=XX)	10 mg (N=XX)	20 mg (N=XX)	40 mg (N=XX)	80 mg (N=XX)	160 mg (N=XX)
		Fast	Fed		

Presentation 2: For prior treatment summaries/histories/disposition

MTR-601					
Placebo	Cohort 1	Cohort 2	Cohort 3	Cohort 4	Cohort 5
(N=XX)	10 mg (N=XX)	20 mg (N=XX)	40 mg (N=XX)	80 mg (N=XX)	160 mg (N=XX)

Overall columns are to be included within the table shells as appropriate. Dose levels in Cohorts may be changed from the values above during the conduct of the trial based on emerging safety and PK data.

For MAD:

MTR-601						
Placebo	Cohort 1	Cohort 2	Cohort 3	Cohort 4	Cohort 5	Cohort 6
(N=XX)	10 mg (N=XX)	20 mg (N=XX)	20 mg (N=XX)	40 mg (N=XX)	80 mg (N=XX)	≤160 mg (N=XX)

The placebo participants from all cohorts in each study stage will be pooled into a single placebo (per SAD or MAD) for all summaries and presentations.

Listings will be sorted in the following order Cohort treatment, subject, parameter, and visit unless otherwise stated. All data will be listed, subjects who were not randomized will be displayed after the randomized treatment.

The 'Screening Number' will be used and represented as 'Subject Number' for all TLFs.

Continuous variables will be summarized by the number of non-missing observations, mean, median, standard deviation, and minimum and maximum.

Categorical variables will be summarized by presenting the frequency and percent. Percentages will be based on the number of subjects in the column header unless otherwise specified in the footnote. For each

QMD Ref: Worldwide-TMP-ST-054-1.0_Effective: 12Aug2022	Governing QMD: Worldwide-SOP-ST-026

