In counting the number of AEs reported, a continuous event (i.e., reported more than once and which did not cease), will be counted only once; non-continuous AE reported several times by the same subject will be counted as multiple events.

In the AE summary tables the system organ class will be order alphabetically and the preferred term within the system organ class will be order in decreasing frequency for the Overall column. In case of tie(s), the preferred term will be ordered alphabetically.

For SAD cohort 2 the AE will be attributed to the treatment as taken based on the event date and the dosing date.

All AEs will be listed for Safety population.

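### In the SAD adverse event tables the Cohort 2 Fast and Fed columns are not like for like, mainly because the cohort's only muscle biopsy falls in the Fed period

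*SAP*

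**What the plan says.** - **Objective.** The primary objective (Protocol 3, SAP 2) is "To assess the safety and tolerability of single and multiple doses of MTR-601 in normal healthy volunteers under fed and fasted conditions". TEAE incidence is one of its endpoints.
- **Columns.** SAP 5.3 has a layout headed "Presentation 1: For on and/or after treatment summaries", with Fast and Fed sub-columns. These belong to Cohort 2, the only cohort dosed in both states. All SAD placebo subjects share one column.
- **Attribution.** SAP 5.16.1: "For SAD cohort 2 the AE will be attributed to the treatment as taken based on the event date and the dosing date".
- **Order.** Level 2 subjects "will be dosed in a fasting state on Day 1 with a subsequent 4-day washout period" and receive the fed dose on Day 6 (Protocol 4.1). The order is the same for everyone.
- **Biopsy.** The Table 2 footnote for Days 6–10 reads "Mandatory muscle biopsy on Day 7 (time 0) only". The Day 1–5 part of Table 2, as supplied, shows none. For the other SAD levels the schedule footnote reads "Mandatory muscle biopsy on Day 2 only". Protocol 2.5 says of the biopsy: "The risks of such a procedure are discomfort/pain and possibly some small post-procedure bleeding".
- **AE collection.** Protocol 4.1.1 ends it for this cohort at the Day 12 call. Protocol Table 8 (section 8.3) continues it for 14 days after the last follow-up.

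**The concern.** The Fast and Fed columns will be read next to each other, and descriptive tables are the only evidence planned for the part of the primary objective that concerns food state. The date rule puts all biopsy pain and bleeding into Fed and none into Fast. An excess of events under Fed, or a low 20 mg Fast rate beside placebo subjects who were all biopsied, could come from the procedure and be taken for an effect of food or of higher exposure. The parts of the SAP available for review contain no common observation window, no separate count of biopsy events and no caveat on the table.

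**Working it through.** **Calendar check.** 30 days of screening plus the Day 12 call gives 42 days, which reproduces the protocol's approximate duration for the two-dose cohort. The AE windows follow:

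- Fast: Day 1 dose to Day 6 dose = 5 days, all in-house.
- Fed: Day 6 dose to Day 12 call = 6 days. Discharge is on Day 10, so the last part rests on a phone call. Ratio 6/5 = 1.2.
- Fed under Table 8: Day 12 + 14 = Day 26, so 20 days. Ratio 20/5 = 4.0.

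**Scheduled post-dose checks** (counted by column position in the Table 2 grid):

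| | Fast | Fed |
|---|---|---|
| Muscle biopsy | 0 | 1 (Day 7) |
| IPSS | 4 (Days 2–5) | 6 (Day 6 at 6 h; Days 7, 8, 9; Day 10 at 0 and 4 h) |
| Urinary ultrasound | 1 (Day 3) | 2 (Day 8; Day 10 at 4 h) |
| Spirometry | 5 | 4 |
| Nerve stimulation | 3 | 3 |

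The laboratory, urinalysis and vital sign rows for Days 1–5 are not in the supplied text and could not be counted.

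**Illustration with no drug effect and no food effect.** Assume a constant background rate r per subject-day and a probability b that a subject reports a biopsy AE. The documents give neither, so both are shown over a range.

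- Fast = 1 − exp(−5r)
- Fed = 1 − (1 − b) × exp(−6r)
- Pooled placebo = 0.8 × [1 − (1 − b) × exp(−6r)] + 0.2 × [1 − (1 − b) × exp(−11r)]. With five SAD cohorts there are 10 placebo subjects; the 2 from Cohort 2 are followed for 11 days and the other 8 for 6 days (Day 1 to the Day 7 call).

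For r = 0.03, Fast = 1 − exp(−0.15) = 13.9%, or 0.84 of 6 subjects.

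| b | Fed | Fed, subjects of 6 | Pooled placebo |
|---|---|---|---|
| 0 | 16.5% | 0.99 | 18.8% |
| 10% | 24.8% | 1.49 | 26.9% |
| 25% | 37.4% | 2.24 | 39.1% |
| 50% | 58.2% | 3.49 | 59.4% |

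Other background rates, window alone (b = 0): 4.9% Fast against 5.8% Fed at r = 0.01, and 39.3% against 45.1% at r = 0.10. With the 20-day window and no biopsy AEs, Fed at r = 0.03 is 1 − exp(−0.6) = 45.1%.

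**Effect of a 96 h cut.** Without biopsy AEs both columns become 1 − exp(−4 × 0.03) = 11.3%. The biopsy is at 24 h, inside the cut. If biopsy AEs at b = 25% stay in, Fed is 1 − 0.75 × exp(−0.12) = 33.5%. The window alone does not solve the problem. By 96 h, scheduled IPSS is 4 against 5 and ultrasound 1 against 1, while spirometry is 5 against 3, because the Day 10 4 h checks fall at 100 h.

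**The case against.** A reader might infer that a planned fed-versus-fasted safety comparison is biased. The documents do not support that. Protocol 9.1 rules out formal hypothesis testing, and the only planned food contrast is pharmacokinetic (SAP 5.14.3.2).

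Nor are the safety columns affected across the board. Laboratory, vital sign and ECG data are tabulated by visit, and SAP 5.2.3 gives Cohort 2 a separate baseline for each period, so matched time points remain comparable. Ultrasound is only listed. Nor is Fed observed more closely throughout: Fast is in-house for longer and has more spirometry. The one-day window gap is worth 0.15 of a subject in six at r = 0.03 (0.99 − 0.84). All of this stands.

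It is also fair that biopsy pain or bleeding would appear under its own preferred term, and that Protocol 8.4.4.4 classes an event clearly due to other factors as not related, which would take it out of the treatment-related tables. That separates the events only in part. The overall, system organ class and severity tables still carry them. The drug acts on skeletal muscle, so thigh pain or weakness after a biopsy could reasonably be judged possibly related. SAP 5.16.1 also counts an event with missing relationship as related.

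Finally, the fixed fasted-then-fed order means that no choice of window can isolate food. That is correct, and it is a reason to say so on the table.

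**Conclusion.** The point holds for the SAD AE and AESI tables. Biopsy-site events can appear only under Fed, and Fast is the one SAD column without a biopsy; Fed is close to the other SAD cohorts and to pooled placebo in this respect. The biopsy is the main driver. The window and the urinary checks are minor on the Day 12 end date, but the window would become large if the Table 8 end date applied.

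What the documents establish are the counts: biopsy 0 against 1, window 5 against 6 days, IPSS 4 against 6, ultrasound 1 against 2, and 16.7 points per subject in a column of six. The percentage gaps are illustrations that rest on assumed background and biopsy-AE rates and on a constant hazard, and should not be quoted as expected results. The problem lies in how a descriptive table will be read, and a cheap change of presentation deals with most of it.

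**What to change.** Amend SAP 5.16.1 and 5.3, which SAP section 5 allows before database lock:

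1. For Cohort 2 Fast and Fed, count TEAEs with onset within a common window after each dose. 96 h works, since subjects are in-house that long in both periods. Put later events on a separate row.
2. Flag biopsy-procedure AEs by a review of term, site and onset that is blind to MTR-601 or placebo. Give the SAD overall and SOC/PT TEAE summaries with and without them. SAD cohorts 1–4 have already had an unblinded interim analysis (Protocol 2.3), so the flagging belongs with staff who have not seen allocation.
3. Show the Cohort 2 placebo subjects by period, or footnote that they contribute two periods to the pooled column. Do not restrict them to the fasted period, which would put unbiopsied time into a column of biopsied subjects.
4. Footnote that food state is confounded with period.
5. Reconcile the AE collection end date between Protocol 4.1.1 and Table 8.

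Cost: a small flagging task, because the AE items in Protocol 8.4.4.1 do not include relationship to a procedure, and a few extra table rows. No new assessments are needed. Some late or biopsy-related events leave the main Fed count but stay visible in their own rows and in the listings.

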5.16.2 Laboratory Data

Descriptive statistics of the observed values and change from baseline (continuous data) will be presented by treatment cohort and visit for each hematology, urinalysis, Coagulation, and serum chemistry parameter. Each measurement (continuous data) will be classed as below, within, or above normal range, based on ranges supplied by the laboratory used. Shift tables in relation to the normal range from baseline to each

QMD Ref: Worldwide-TMP-ST-054-1.0_Effective: 12Aug2022	Governing QMD: Worldwide-SOP-ST-026
Confidentiality Statement This document is the property of Worldwide Clinical Trials Inc. and may not be duplicated, copied, altered or removed from company without prior approval from Worldwide Quality Assurance or in compliance with Worldwide Standard Operating Procedures.	

Worldwide Clinical Trials Controlled Quality Management Document			
		Sponsor:	MTR-601-NHV-101
		Protocol Number:	Motric Bio
STATISTICAL ANALYSIS PLAN			

follow-up visit and treatment cohort will be presented. All laboratory parameters will be listed in the order as per protocol (Table 8).

Laboratory tests will be reported in international system of units (SI) and will be used for analysis.

A listing of any clinically significant laboratory measurements recorded throughout the study will be presented.

All other laboratory data including Pregnancy test (Urine or serum) or FSH, Urine drug screen for cotinine, alcohol and drugs of abuse, Serology data, liver function tests will be listed in the order as per protocol (Table 8 Safety Assessments).

5.16.3 Vital Signs

Descriptive statistics for observed values and changes from baseline in the following vital signs will be presented by treatment cohort and visit:

- Systolic blood pressure (mmHg)
- Diastolic blood pressure (mmHg)
- Heart rate (bpm)
- Respiration rate (breath / min)
- Body temperature (degrees Celsius)

All Vital Signs data, including details of any abnormalities, will be listed.

5.16.4 Electrocardiogram Data

Descriptive statistics for observed values and changes from baseline in the following ECG variables will be tabulated by treatment cohort and visit:

- Ventricular rate (bpm)
- PR interval (ms)
- RR interval (ms)
- QRS complex (ms)
- QT interval (ms)
- QTc interval (ms)
- QTcB interval (ms) [Bazett's formula - QTcB]
- QTcF interval (ms) [Fridericia's formula - QTcF]

QMD Ref: Worldwide-TMP-ST-054-1.0_Effective: 12Aug2022	Governing QMD: Worldwide-SOP-ST-026
Confidentiality Statement This document is the property of Worldwide Clinical Trials Inc. and may not be duplicated, copied, altered or removed from company without prior approval from Worldwide Quality Assurance or in compliance with Worldwide Standard Operating Procedures.	

Worldwide Clinical Trials Controlled Quality Management Document			
		Sponsor:	MTR-601-NHV-101
		Protocol Number:	Motric Bio
STATISTICAL ANALYSIS PLAN			

Shift tables in relation to the overall interpretation (Normal, Abnormal NCS, and Abnormal CS) from baseline to EOS/ET visit by treatment cohort will be presented.

All ECG data, including details of any abnormalities, will be listed.

